**Table 2: Randomization Numbers and Treatment Assignment**

Cohort	Randomization Numbers	Treatment Assignment	
1	101-108	0.05 mg/kg HM15912 (N = 6)	Placebo (N = 2)
2	201-208	0.1 mg/kg HM15912 (N = 6)	Placebo (N = 2)
3	301-308	0.5 mg/kg HM15912 (N = 6)	Placebo (N = 2)
4	401-408	1.0 mg/kg HM15912 (N = 6)	Placebo (N = 2)
5	501-508	1.5 mg/kg HM15912 (N = 6)	Placebo (N = 2)

Once a randomization number has been allocated to one subject, it may not be assigned to another subject. If subjects withdraw prematurely from the study and are replaced under the direction of the Sponsor, then a replacement randomization number will be assigned when a replaced subject has successfully completed screening. A replacement randomization code will be generated such that replacement subjects are assigned to the same treatment as the discontinued subjects. The replacement randomization code will differ only in randomization numbers. It is composed of 4 digits by adding "1" in front of the randomization number for a withdrawn subject. For example, if Subject 202 withdraws and is replaced, then the randomization number for the replacement subject will be 1202.

The study blind should not be broken except in a medical emergency (where knowledge of the IP administered would affect the treatment of the emergency), or if dose limiting toxicities occur or if it is necessary for dose escalation decisions. The decision to break the blind will be made by the Principal Investigator on a case-by-case basis. The Investigator or the Principal Investigator will contact Hanmi Pharmaceutical Co., Ltd. and deliver related documents when breaking the blind. The results of breaking the blind for each subject will not be revealed. The Investigator or the Principal Investigator will record blind-breaking dates and reasons in the CRF.

If blinding is not maintained in the Investigator, the institution's staff or subjects, the subject must be withdrawn. If blinding is accidentally broken during the study or blinding is broken before completion of the study due to SAEs, the Investigator must record this and rapidly report to Hanmi Pharmaceutical Co., Ltd. However, if blinding is broken for ethical reasons or blind breaking is seen to have little effect on the subject's safety, the subject may continue to participate in the clinical study in the judgement of the Investigator after discussing with Hanmi Pharmaceutical Co., Ltd.

After database lock, the overall randomization code will be broken.

### 2.3 Sample Size and Power

Due to exploratory nature of this study, sample size 8 subjects (6:2) is empirically determined and consistent with typical sample sizes used for similar studies to assess PK and safety data. No formal sample size calculation will be performed.

### 3. STUDY OBJECTIVES

#### 3.1 Primary Objectives and Endpoints

To assess the safety and tolerability of HM15912 after single SC doses, regarding:

- General safety variables: Adverse event (AE) assessments; clinical laboratory tests (hematology, clinical chemistry, coagulation and urinalysis); vital signs (blood pressure [BP], pulse, tympanic temperature and respiratory rate [RR]); 12-lead electrocardiogram (ECG); physical examinations
- Specific safety variables: Injection site assessments; immunogenicity assessments (ADA, Nab and anti-PEG) (performed only if analysis is necessary)

#### 3.2 Secondary Objectives and Endpoints

To assess the PK profile of HM15912 after single SC doses, regarding:

- $C_{max}$ : Maximum serum HM15912 concentration determined from the concentration-time profile
- $T_{max}$ : Time of maximum serum HM15912 concentration determined from the concentration-time profile
- $AUC_{0-t}$ : Area under the concentration-time curve from predose (time 0) to the last quantifiable concentration
- $AUC_{inf}$ : Area under the concentration-time curve from predose (time 0) extrapolated to infinite time ( $AUC_{0-t} + C_{last}/\lambda_z$ ) calculated using the linear-log trapezoidal rule
- $AUC_{%extrap}$ : Percentage of  $AUC_{inf}$  that is due to extrapolation beyond  $t_{last}$
- $\lambda_z$ : The terminal elimination rate constant determined by selection of at least 3 data points on the terminal phase of the concentration-time curve
- $t_{1/2}$ : Terminal elimination half-life calculated as:  $\ln 2/\lambda_z$
- $CL/F$ : Total body clearance calculated as: Dose/ $AUC_{inf}$
- $V_z/F$ : Apparent volume of distribution calculated as: Dose/( $AUC_{inf} * \lambda_z$ )

#### 3.3 Exploratory Objectives and Endpoints

To assess the PD properties of HM15912 after single SC doses, regarding:

- Blood plasma citrulline
- Albumin, prealbumin
- Fasting lipid panel (total cholesterol, triglycerides, low-density lipoprotein [LDL], high-density lipoprotein [HDL], very low-density lipoprotein [VLDL], free fatty acid [FFA])
- Blood glucose-related panel (fasting plasma glucose, gastric inhibitory polypeptide [GIP], glucagon-like peptide-1 [GLP-1], C-peptide, glucagon, insulin)

- Insulin-like growth factor-1 (IGF-1) and keratinocyte growth factor (KGF)

## 4. ANALYSIS SET

An analysis sets classification meeting will be arranged to discuss the outputs and to decide which patients and/or patient data will be excluded from certain analyses. Decisions made regarding the exclusion of patients and/or patient data from analyses will be made after the database lock and before the unblinding and will be documented and approved.

Prior to unblinding, analysis populations will be defined through blinded data review. In this clinical study, the PK population is subject to PK assessments whereas the PD population is subject to PD assessments. The safety population is subject to all other analyses unless described otherwise. Each analysis population is included in the analyses, based on the actually administered IP and dosage.

### 4.1 Safety Set

All randomized subjects who received at least 1 dose of the IP, HM15912 or placebo (actual treatment).

### 4.2 Pharmacokinetic Analysis Set

All subjects who are treated HM15912 (actual treatment) with at least one quantifiable HM15912 concentration.

### 4.3 Pharmacodynamics Analysis Set

All randomized subjects who received at least 1 dose of the IP, HM15912 or placebo. (actual treatment)

## 5. STUDY SUBJECT

Study subject data will be summarized by dose level, with pooled placebo using the Safety Set.

### 5.1 Subject Disposition

Subjects disposition will be summarized into the numbers and percentages of subjects dosed after randomization, subjects included in each analysis population, subjects completing the study, subjects who were withdrawn (including reasons for withdrawal) and subjects who have seriously violated the protocol.

### 5.2 Demographic and Baseline Characteristics

Demographic data, such as age, sex, height, weight, and BMI, and descriptive statistics of baseline characteristics or the number and percentage of subjects by category will be provided.

### 5.3 Medical History

Medical history is any significant medical condition or disease that is present at study start (signing of informed consent). The medical history recorded through clinically significant laboratory, electrocardiogram (ECG), or physical examination (PE) abnormalities noted at screening examination will be listed.

Medical history will be coded using Medical Dictionary for Regulatory Activities (MedDRA, version 22.0 or over) and summarized by System Organ Class (SOC) and Preferred Term (PT) for the Safety Set. Medical history data will be listed by subject, description of the disease/procedure, MedDRA SOC, PT, start date and stop date (or ongoing if applicable).

### 5.4 Subject Eligibility and Withdrawal Criteria

Subject eligibility and subjects who meet withdrawal criteria will be presented in listings.

### 5.5 Exposure

A listing of IP administration will be created by subject and will include the date and time of administration and dosage, etc.

### 5.6 Concomitant Medication

Concomitant medication is medication given in addition to the study medication (including over-the-counter medications, herbal medications, and vitamin supplements) administered between screening and follow-up. Medication will be categorized into the three following types:

- Prior concomitant medication is defined as any medications that start before the date of

dosing of study medication and continue beyond that date.

- New concomitant medication is defined as any medications that start after the date of dosing of study medication, including those started in the follow-up period.
- Prior medication is defined as any non-study medication that stops before the date of dosing of study medication.

The WHO DRUG Dictionary Global (March 2019 or over) will be used to categorize the verbatim descriptions of medications into the Anatomic Therapeutic Chemistry (ATC) classification system. Each verbatim name will be classified by anatomical main group (ATC level 1), therapeutic subgroup (ATC level 2), pharmacological subgroup (ATC level 3), chemical subgroup (ATC level 4), and trade name.

Drug administration dates and times will be listed for each subject and the number and percentage of subjects receiving concomitant medications (including both prior and new concomitant medications) will be summarized and by ATC classification (ATC level 2 and level 4) for the Safety Set. Pre-treatment medication administered during the study will only be listed.

### **5.7 Protocol Deviations**

All the protocol deviations will be listed by subject. Category of important/non-important will be included in the listing. Protocol deviations will be handled in accordance with ICH guidelines and local regulation for management. Important protocol deviations will be identified prior to database lock and will be summarized for the Safety Set.

## 6. Statistical Methods

### 6.1 General Considerations

PK, PD, and Safety analyses will be performed with the PK Analysis Set, PD Analysis Set, and Safety Set, respectively. Placebo subjects will be pooled in summaries and listings.

Exploratory analysis may be conducted to assess any patterns due to COVID-19.

All data collected during the study will be listed using the Safety Set.

#### 6.1.1 Statistical Notation and Presentation

The continuous variables will be summarized by number of subjects (n), mean, standard deviation (SD), median, minimum (min), and maximum (max). Where appropriate, change from baseline will also be summarized. For categorical variables, the number and percentage of subjects in each category will be provided. For log-normal distributed data, geometric mean, standard error (SE) of the geometric mean, and coefficient of variation (CV) will also be provided. The geometric mean is calculated as the exponential of the arithmetic mean calculated from data on a log scale. The CV is calculated as  $CV\% = 100\% * \sqrt{exp(\sigma^2) - 1}$ , where  $\sigma$  is the SD of the data on the natural log scale. Minimum and maximum values will be rounded to the precision of the original value. Means, least squares (LS) means, and medians will be rounded to 1 decimal place greater than the precision of the original value. SDs, SEs, and confidence intervals (CIs) will be rounded to 2 decimal places greater than the precision of the original value. Percentages for summarizing categorical data will be rounded to one decimal place. P-values will be presented with 4 decimal places and values less than 0.0001 will be presented as <.0001.

All inferential statistical testing will be two-sided and conducted at the 0.05 significance level, unless specified otherwise. No multiplicity adjustment is planned for this study.

#### 6.1.2 Handling of Multiple Observations or Out of Window Observations

### 6.1.3 Handling of Missing and Partial Dates

In cases of incomplete dates for adverse events (AEs) or concomitant medications, the missing component(s) will be assumed as the most conservative value(s) possible. The imputation rule are designed to conservatively capture AEs as treatment-emergent AEs (TEAEs) and medications as concomitant. For example, the following algorithm for missing start date of AEs will be followed:

[REDACTED]

Adverse events and medications with missing or partial end dates will be imputed to conservatively capture treatment-emergent or concomitant status.

Date imputation will only be used for computational purposes; e.g., treatment-emergent status or identifying concomitant medications. Actual data values, as they appear in the clinical database, will be shown in the data listings.

Missing visits due to COVID-19 will be listed with the reason for missing.

### 6.1.4 Handling of Outliers and Unquantifiable Measurements

Prior to unblinding, PK data will be reviewed by the PK scientist and statistician to assess whether individual concentration values are inconsistent with other values from the same subject or if there are errors with the samples. Determination of data points subject to re-analysis or removal from determination of PK parameters (i.e., implausible data) will be documented prior to unblinding. PK and PD parameter results will also be reviewed by appropriate representatives and a determination of plausibility will be made. Individual subject results deemed implausible may be removed prior to summarization of PK and PD parameter results by treatment group. Removal of individual subject PK/PD parameter results will be documented.

The following rules will be applied when blood samples are assayed as below the limit of quantitation (BLQ) or if individual concentration results are deemed implausible prior to database lock:

[REDACTED]

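### SAP 6.1.4 lets individual PK and PD parameter results be dropped from the summaries on a plausibility judgment alone, with no assignable cause required and no summary that keeps them

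*SAP*

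**What the plan says.** SAP 6.1.4 sets out two separate reviews.

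- **Single concentrations.** The PK scientist and the statistician check, before unblinding, whether "individual concentration values are inconsistent with other values from the same subject or if there are errors with the samples". The timing is explicit: "Determination of data points subject to re-analysis or removal from determination of PK parameters (i.e., implausible data) will be documented prior to unblinding".
- **Derived results.** The next step is looser: "PK and PD parameter results will also be reviewed by appropriate representatives and a determination of plausibility will be made". The consequence follows: "Individual subject results deemed implausible may be removed prior to summarization of PK and PD parameter results by treatment group". The only condition attached is "Removal of individual subject PK/PD parameter results will be documented".

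Two general provisions also apply. SAP 4 says "Decisions made regarding the exclusion of patients and/or patient data from analyses will be made after the database lock and before the unblinding", and requires those decisions to be documented and approved. SAP 6.1 says "All data collected during the study will be listed using the Safety Set".

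Part of 6.1.4 is redacted. The sentence that introduces the redacted rules concerns samples below the quantitation limit and implausible concentrations, not derived parameters. SAP 6.3.2 does give numerical acceptance conditions, but only for the terminal slope and the parameters that depend on it, and the pharmacometrist may override them.

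**The concern.** The concentration step has named reviewers and stated grounds. The parameter step has neither. A Cmax, an AUC or a biomarker result can leave the dose-level table because it does not look right, although no one has found a fault in dosing, sampling, handling or assay. The SAP plans no companion table that keeps the value.

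Selecting on the outcome is what does the damage. In a group of six, a genuine extreme carries much of the information on between-subject variability, and describing exposure is the study's secondary objective. Protocol 1.2 says the results will inform design and dose selection in later studies. A mean and CV pulled towards what the reviewers expected would be carried into that planning.

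**Working it through.** **Inputs from the documents.** There are 6 active and 2 placebo subjects per cohort and about 5 cohorts (SAP 2.1). SAP 6.1.1 calls for n, mean, SD, median, minimum and maximum, and for log-normal data also the geometric mean, its SE and the CV, computed as sqrt(exp(s²) − 1) with s the log-scale SD. The documents give no CV, no removal rate and no sample-size calculation, so there is no stated figure to reproduce.

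**Assumptions, not in the documents.** Exposure is log-normal with true between-subject CV of 30%, 40% or 50%, and one genuine value per dose group is removed.

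**Weight of one subject.** 1/6 = 16.7% of a dose group.

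**Geometric mean when the true highest of six is dropped.** The expected maximum of six standard normal values is 1.267. Dropping it moves the mean of the remaining five by −1.267/5 = −0.253 log-scale SDs. With σ = sqrt(ln(1 + CV²)):

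| True CV | σ | exp(−0.253σ) − 1 |
|---|---|---|
| 30% | 0.294 | −7.2% |
| 40% | 0.385 | −9.3% |
| 50% | 0.472 | −11.3% |

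**Variability (simulated samples of six).** The average log-scale SD falls to 0.82 of its full-data value if the highest is dropped, and to 0.71 if the value farthest from the group mean is dropped. These ratios do not depend on the true CV. The average reported CV, using the SAP formula, is:

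| True CV | All six kept | Highest dropped | Farthest from mean dropped | One dropped at random |
|---|---|---|---|---|
| 30% | 28.7% | 23.3% | 20.0% | 28.4% |
| 40% | 38.4% | 31.0% | 26.6% | 38.0% |
| 50% | 48.3% | 38.7% | 33.1% | 47.9% |

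The last column is the control. Losing a subject for a reason unrelated to the value hardly changes the CV, so the shrinkage comes from selecting on the value and not from the smaller n.

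**Dose proportionality.** SAP 6.3.3 requires the 90% CI for the dose-normalized ratio to lie within 0.8 to 1.25. Over the planned 30-fold range (0.05 to 1.5 mg/kg) this is a slope margin of ln(1.25)/ln(30) = 0.066. I used the planned mg/kg levels as regressor, whereas the SAP uses each subject's dose in mg. The sum of squares of log dose for 5 × 6 subjects is 52.1. At CV 30% the slope SE is 0.294/sqrt(52.1) = 0.041, and the 90% CI half-width is 1.701 × 0.0407 = 0.069, already wider than the margin with nothing removed. Dropping the highest value at the top dose moves the slope by about −0.012, which is 0.29 of one SE. In 200,000 simulated trials with true slope 1, proportionality was declared in 4.6% with all data and 4.4% after removal at CV 30%, and in about 0.1% either way at CV 40%. The conclusion is practically unchanged.

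**The case against.** The case for leaving the text alone has real substance. Removal is permitted, not required. Nothing in 6.1.4 says that size by itself is the criterion; it asks for a review and a determination. SAP 4 covers patient data in general, so exclusions of parameter results also fall before unblinding, with documentation and approval. The summary would show n = 5. Removing a derived parameter does not in itself remove that subject's concentrations from the individual plots of SAP 6.3.1. If the value is a true error, dropping it does not understate variability. PK is secondary, PD exploratory, and the summaries are largely descriptive. For PD, pooled placebo has 2 × 5 = 10 subjects if all cohorts enrol, so one removal matters less there.

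All of this stands, and it makes the problem conditional. It does not supply the missing criterion or the missing all-values summary.

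A reader might infer three stronger points that the documents do not support.

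- **A timing conflict.** One sentence of 6.1.4 says "if individual concentration results are deemed implausible prior to database lock", while SAP 4 puts exclusions after lock. The first phrase introduces redacted handling rules for unquantifiable and implausible concentrations. SAP 4 concerns which patients or data are excluded from analyses, and its decisions come before unblinding. No consequence can be shown from the readable text.
- **A concealed safety signal.** Safety data have their own listings and summaries under SAP 6.2. The escalation review in SAP 7 works from listings of adverse events and laboratory data and, if available, PK concentrations. It does not depend on the final parameter summaries. Albumin, prealbumin, lipids and fasting glucose also belong to the clinical laboratory tests.
- **A distorted proportionality verdict.** The SAP does not say that results removed before summarization also leave the power model, and the effect on the declaration is negligible even if they do.

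**Conclusion.** The point holds for the dose-level PK and PD summaries. SAP 6.1.4 permits removal of derived results on judgment alone, without an assignable cause and without a summary that keeps them. If a genuine maximum of six is dropped, the geometric mean is understated by about 7% to 11% and the log-scale SD falls to about 82% of its value. If the value farthest from the mean is dropped, the SD falls to about 71%. These figures rest on log-normal data, assumed CVs of 30% to 50%, and one genuine value removed per affected group. They do not say how often removal would occur. The safeguards make a removal traceable and limit treatment-aware choices, but they do not correct the reported mean and CV. This is a worthwhile correction to the analysis plan, not a threat to the primary safety objective.

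**What to change.** In SAP 6.1.4, replace the open plausibility provision for parameter results with a rule. A result leaves the main summary only for a documented dosing, sampling, handling or assay error, or because it fails the terminal-slope criteria already stated in SAP 6.3.2. The decision is taken under the SAP 4 process before unblinding. Other unusual results stay in the main tables. For any removal, present the affected PK or PD summary and the dose-proportionality estimate with and without the value; this also settles whether removed results leave the power model.

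The cost is a few sentences of SAP text and an occasional duplicate table. Reported CVs may be larger. Study conduct and sample size do not change.

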### 6.1.5 Study Baseline

Baseline will be defined as the last non-missing observation obtained prior to the administration of the study drug.

## 6.2 Safety Analyses

Safety data will be summarized by treatment, with pooled placebo. All safety data will be listed.

### 6.2.1 Adverse Events

Adverse events (AEs) will be coded using MedDRA, version 22.0 or over. All AEs will be listed.

AEs with onset on or after the date of informed consent but before the date of dosing of study medication will be considered pre-treatment AEs. Pre-treatment AE will be listed only.

AEs with onset date/time on or after receiving the dosing of study medication, or pre-existing AEs that increase severity on or after receiving the dosing of study medication will be considered as TEAE.

The number and percentage of subjects who experience one or more AEs will be tabulated by SOC and PT and by SOC, PT and maximum severity for each cohort and overall. The sorting is by descending frequency of SOC and PT. TEAEs that are related to study medication per investigator's decision, TEAEs leading to study discontinuation, and TEAEs that are serious (treatment-emergent SAEs), will be summarized similarly.

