PK data will only be reviewed if available. After review of the PK data from the preceding or current cohorts, changes in time points for PK collection, clinical laboratory assessments, and PD collection may be required and will be approved by the MFDS and the IRB.

If dose escalation is stopped based on available blinded safety data, the current dose level will be considered as the minimum intolerable dose (MID). The dose just below the MID will be regarded as the maximum tolerated dose (MTD). If the dose escalation is stopped due to reaching exposure limit without dose-limiting safety findings, the MTD cannot be determined. Dose de-escalation may occur in the last cohort or additional cohorts to further refine clinically relevant dose levels.

Stopping rules are described in Section 3.4.

The study will be comprised of:

- A Screening visit up to 28 days before dosing

- An inpatient assessment period of approximately 8 days, with admission to the institution on Day-1, dosing on Day 1, and discharge on Day 7 once the planned schedule is completed
- Two Outpatient visits on Day 8 (\pm 4 hours), Day 10 (\pm 1 day), Day 17 (\pm 1 day) and Day 30 (\pm 3 days)
- A final Follow-up visit on Day 44 (\pm 3 days)

The total duration of the clinical study per subject will be up to approximately 72 days, including the Screening period.

Procedures related to the clinical study are detailed in the Schedule of Assessments, the PK Sampling Schedule, the Citrulline Sampling Schedule, and the PD Sampling Schedule ([Table 1-1 and 1-2](#), [Table 2-1 and 2-2](#), [Table 3-1 and 3-2](#), respectively).

Doses will be administered via SC injection to subjects in approximately 5 dose cohorts. Additional cohorts may be enrolled and proceed at a dose higher or lower than the planned maximum dose of 1.5 mg/kg, if deemed appropriate by the Principal Investigator and the Sponsor, but cohorts are planned as follows:

Table 4 Cohorts and Dose Administration

Cohorts	Number of Subjects	Treatment ¹
Cohort 1	N = 6	HM15912 0.05 mg/kg
	N = 2	Placebo
Cohort 2	N = 6	HM15912 0.1 mg/kg
	N = 2	Placebo
Cohort 3	N = 6	HM15912 0.5 mg/kg
	N = 2	Placebo
Cohort 4	N = 6	HM15912 1.0 mg/kg
	N = 2	Placebo
Cohort 5	N = 6	HM15912 1.5 mg/kg
	N = 2	Placebo

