6.2. Safety Variables

6.2.1. Adverse Events

AE reporting will begin for each subject from the date he/she signs the ICF and will continue until the Follow-up visit.

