7.5. Follow-up

The Follow-up visit will occur on Day 44 (\pm 3 days) of the clinical study.

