8.7. Safety Analyses

8.7.1. Adverse Events

Summarization and analysis of AEs will be conducted for treatment emergent adverse events (TEAE). TEAEs are defined as AEs that did not exist before IP administration but occurred after IP administration, or AEs that worsened after IP administration even if they existed before IP administration.

The reported AEs will be coded according to the SOC and PT of MedDRA, and the number of subjects and percentage for AEs after IP administration, AEs related to the IP, SAEs, severe AEs, AEs that caused study withdrawal, and AEs coded for injection site reactions will be provided.

All AEs, SAEs, AEs that caused study withdrawal, and injection site reactions will be listed by subject.

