8.10. Interim Analyses

No formal interim analysis is planned. However, available blinded safety and tolerability (including PK/PD data if available) from each cohort (Day-1 to Day 17) will be evaluated in a dose escalation review meeting by the Principal Investigator and the Sponsor. The data review will take place before dose escalation can proceed. Screening for the next cohort may be conducted even before proceeding to the next cohort is determined, but the IP should be administered after proceeding to the next cohort is determined.

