PK data will only be reviewed if available. After review of the PK data from preceding or current cohorts, changes in time points for PK collection, clinical laboratory assessments, and PD collection may be required and will be approved by the MFDS and the IRB.

If dose escalation is stopped based on available blinded safety data, the current dose level will be considered as the minimum intolerable dose (MID). The dose just below the MID will be regarded as the maximum tolerated dose (MTD). If the dose escalation is stopped due to reaching exposure limit without dose-limiting safety findings, the MTD cannot be determined. Dose de-escalation may occur in the last cohort or additional cohorts to further refine clinically relevant dose levels.

The study will be comprised of:

- A Screening visit up to 28 days before dosing
- An inpatient assessment period of approximately 8 days, with admission to the institution on Day -1, dosing on Day 1 and discharge on Day 7 once the planned schedule is completed
- For Cohort 1~3
  - Two Outpatient visits on Day 10 ( $\pm$  1 day) and Day 17 ( $\pm$  1 day)
  - A final Follow-up visit on Day 30 ( $\pm$  3 days)
- For Cohort 4~5
  - Four Outpatient visits on Day 8 ( $\pm$  4 hours), Day 10 ( $\pm$  1 day), Day 17 ( $\pm$  1 day) and Day 30 ( $\pm$  3 days)
  - A final Follow-up visit on Day 44 ( $\pm$  3 days)

The total duration of the clinical study per subject will be up to approximately 58 days for Cohort1-3 and 72 days for Cohort4-5, including the Screening period.

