Box plots of  $C_{max}$ ,  $AUC_{0-last}$  and  $AUC_{0-inf}$  for each cohort may be generated. The planned last sampling

time of each cohort will be informed as an annotation at  $AUC_{0-\text{last}}$  of summary stat and box plot as planned last sampling times for Cohort 1-3 and Cohort 4-5 are different as Day 30 and Day 44, respectively.

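### The TEAE tables set dose groups followed for 29 days beside dose groups followed for 43 days, with no common observation window

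*SAP*

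**What the plan says.** Protocol 6.2.1 starts adverse event reporting at consent and says it "will continue until the Follow-up visit". SAP 2.1 and Protocol Tables 1-1 and 1-2 place that visit at Day 30 for Cohorts 1-3 and Day 44 for Cohorts 4-5. SAP 2.1 gives the resulting time in study as "58 days for Cohort1-3 and 72 days for Cohort4-5".

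Neither definition of a treatment-emergent event has an upper time limit. Protocol 8.7.1 reads "TEAEs are defined as AEs that did not exist before IP administration but occurred after IP administration", and adds events that worsen after dosing; SAP 6.2.1 is equivalent. The summary is a count and percentage of subjects, "by SOC and PT and by SOC, PT and maximum severity for each cohort and overall". SAP 6.2 and Protocol 8.2 pool placebo subjects across cohorts into one separate group.

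The SAP does recognise the unequal schedule elsewhere. Section 6.3.2 annotates AUC0-last because "planned last sampling times for Cohort 1-3 and Cohort 4-5 are different as Day 30 and Day 44". The readable text has no matching cut-off, rate or footnote for adverse events.

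Two wording points are connected. The phrase about cohorts in SAP 6.2.1 does not match the grouping by treatment with pooled placebo in SAP 6.2. And Protocol 3.1 ("A final Follow-up visit on Day 44") and 7.5 ("The Follow-up visit will occur on Day 44") give a single day with no split by cohort, which conflicts with Protocol Table 1-1 and SAP 2.1.

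**The concern.** Adverse events are one of the primary safety variables, and the table by dose is where a reader looks for a dose trend. A crude percentage with at least one event can only rise with longer observation. Here the longer observation falls on exactly the two highest doses, so time and dose are confounded. Even if the drug did nothing, the expected percentages at 1.0 and 1.5 mg/kg would be at least as high as those below.

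Pooled placebo does not repair this. With 6 subjects on the short schedule and 4 on the long one, it matches neither set of dose groups. The lower doses would tend to look better than placebo and the top doses worse, which is the pattern of a dose response.

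Late events cannot be assumed away. Protocol 1.1 describes a molecule designed for a prolonged half-life, and Protocol 7.8.2 foresees delayed hypersensitivity some weeks after dosing. Clinically significant laboratory and ECG findings count as adverse events (Protocol 6.2.2 and 6.2.4), and only Cohorts 4-5 have these tests at Day 44.

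**Working it through.** **The plan's own durations.** Screening of up to 28 days plus the last study day gives 28 + 30 = 58 and 28 + 44 = 72 days. Both agree with SAP 2.1.

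**Time after dosing.** Protocol Tables 3-1 and 3-2 put the last visits at 696 h and 1032 h: 696/24 = 29 days and 1032/24 = 43 days. The ratio is 43/29 = 1.48. With the ±3-day windows the ranges are 26-32 and 40-46 days. They do not overlap, so among subjects who complete the schedule the dose group determines the follow-up length.

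**Pooled placebo.** Two placebo subjects per cohort give 6 at 29 days and 4 at 43. The mean is (6×29 + 4×43)/10 = 34.6 days, between the two.

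**Size of the artefact.** The documents give no event rate, so the 29-day risk of any event, p29, is assumed to be 10-50% and the same in every group (no drug effect).

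- Constant hazard: λ = −ln(1 − p29)/29 and p43 = 1 − exp(−43λ).
- Pooled placebo: (6·p29 + 4·p43)/10.
- Falling hazard: h(t) = h0·2^(−t/h), with h0 set to give the same p29, for halving times h of 14 and 7 days.

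| p29 (assumed) | p43, constant hazard | Step, points | Subjects in 6 | Subjects in 12 | Pooled placebo | Step, halving every 14 d | Step, halving every 7 d |
|---|---|---|---|---|---|---|---|
| 10% | 14.5% | 4.5 | 0.27 | 0.54 | 11.8% | 1.5 | 0.4 |
| 20% | 28.2% | 8.2 | 0.49 | 0.98 | 23.3% | 2.7 | 0.8 |
| 30% | 41.1% | 11.1 | 0.66 | 1.33 | 34.4% | 3.8 | 1.1 |
| 40% | 53.1% | 13.1 | 0.79 | 1.57 | 45.2% | 4.6 | 1.4 |
| 50% | 64.2% | 14.2 | 0.85 | 1.71 | 55.7% | 5.1 | 1.5 |

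Under a constant hazard the top doses sit 2.7-8.5 points above pooled placebo and the lower doses 1.8-5.7 points below it.

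**Scale against chance.** At p29 = 20%, the standard error of the difference between 18 and 12 active subjects is √(0.20×0.80/18 + 0.282×0.718/12) ≈ 0.16. The 8.2-point step is about half of that.

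**After a common window.** The follow-up ratio becomes 29/29 = 1, and the step due to planned follow-up length is zero.

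**The case against.** The strongest reply is that nothing turns on this table. The study is descriptive, with no sample size calculation and no test on adverse events. The escalation review covers the same period throughout: data "from each cohort (Day-1 to Day 17) will be evaluated in a dose escalation review meeting". One subject in 6 is 16.7 points, more than the largest artefact in the table above. The calculation is also for any event, whereas the quoted tables are by system organ class and preferred term. For a single term with an assumed 29-day risk of 2-5%, the constant-hazard step is only 0.95-2.3 points, or 0.06-0.14 of a subject in 6. If no first events occur after Day 30, it is zero. Finally, all events are listed with onset dates, so a careful reader could find the late ones.

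All of this stands as a limit on the size. It does not remove the problem: chance has no preferred direction, whereas this difference follows dose, and descriptive tables are the only adverse event comparison planned.

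Three narrower points also deserve an answer.

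- **Unreadable text.** SAP 6.1.2 and part of 6.1.3 cannot be read, so the absence of a window is shown only for the readable text. Their headings and the revision history point to multiple observations, partial dates and COVID-19, which makes an adverse event window there unlikely.
- **Imperfect cut.** A cut at the Day 30 visit keeps the ±3-day variation and the additional Day 8 visit in Cohorts 4-5 (four post-discharge contacts through Day 30 against three). It removes the 14 extra days, not every difference in ascertainment.
- **Rates per subject-day.** These are an alternative, with planned denominators of 18×29 = 522, 12×43 = 516 and 346 for placebo. But if events come early they overcorrect: with no event after Day 30 and no drug effect, the top-dose rate would be 29/43 = 0.67 of the lower-dose rate.

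**Conclusion.** The concern holds. As written, the plan yields dose columns whose observation time differs systematically with dose (29 against 43 days) and a placebo column that matches neither. For any event, the artefact is 4.5-14.2 points under a constant hazard, 1.5-5.1 points if the hazard halves every 14 days, and 0.4-1.5 points if it halves every 7 days. These figures rest on assumed 29-day risks of 10-50%, no drug effect, and the cohort-specific schedule. If every cohort were followed to Day 44, as Protocol 3.1 and 7.5 read literally, planned follow-up would not differ, which is why those passages must be reconciled.

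It should be fixed because the remedy is cheap and the bias is aligned with dose in a primary safety summary. Escalation decisions and formal tests are not at risk. The wording about each cohort and overall is loose rather than a prescribed 8-subject column, because SAP 6.2 and Protocol 8.2 already keep placebo separate.

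**What to change.** In SAP 6.2.1:

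1. Keep the full-follow-up TEAE table, and footnote the Day 30/Day 44 difference on it, as 6.3.2 does for AUC0-last.
2. Add a TEAE table by HM15912 dose level and pooled placebo, limited to onset (or worsening) through the Day 30 visit in every cohort, and name it as the basis for comparing doses.
3. Show events with onset after the Day 30 visit separately for Cohorts 4-5, including their 4 placebo subjects, so that late events stay visible.
4. Reword the grouping as each HM15912 dose level, all HM15912, and pooled placebo.

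Separately, reconcile Protocol 3.1 and 7.5 with Protocol Table 1-1 and SAP 2.1 on the Follow-up day by cohort.

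The cost is SAP wording, one onset-date filter, one extra table, a short late-event display and a footnote. Onset dates are already recorded (Protocol 6.2.1.2), so no new data are needed, and no event leaves the full table or the listings.
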